6.13. Participants previously randomized to control group

Participants enrolled in this trial prior to amendment 7.0 of this protocol who were randomized to the control (no treatment) group will be offered treatment if they still meet the entry criteria for this trial (i.e. HBV DNA and ALT results from the most recent IT trial visit meet the inclusion and exclusion criteria listed in sections 4.1 and 4.2), and are willing to receive treatment. These participants will be reconsented prior to starting treatment and follow the visit schedule and assessment beginning with baseline (Day 0) visit.

Participants who no longer meet entry criteria for this trial or are not interested in receiving treatment will complete a Termination Visit at the next scheduled visit for the control (no treatment) group. The procedures to be followed for this Termination Visit will be those specified for the Week 48 visit.

7. Adverse events and toxicity management

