7.5. Adverse events – definition and management

7.5.1. Definitions

An adverse event (AE) is any adverse change from the participant's baseline (pre-treatment) condition, including intercurrent illness which occurs during the course of the trial, after the consent form has been signed, whether the event is considered related to treatment or not.

The modified World Health Organization (WHO) grading system will be used for grading severity of AEs. For AEs not outlined in the modified WHO grading system, study specific definitions will be identified in the Manual of Operation (MOP).

A serious adverse event is an untoward medical occurrence that results in any of the following:

1. Death
2. Is life threatening (risk of death at the time of the event)
3. Requires in-patient hospitalization or prolongation of existing hospitalization
4. Results in persistent or significant disability/incapacity
5. Congenital abnormality or birth defect

Important medical events that do not result in one of the events listed above may be considered a serious adverse event when, based upon appropriate medical judgment, they may jeopardize the participant and may require medical or surgical intervention to prevent one of the outcomes listed above.

A serious adverse event which is unexpected and is related will require expedited reporting to the DCC and the NIDDK and appropriate oversight committees or entities.

Disease related outcomes, such as the following, will not be considered to be serious adverse

events:

1. Development of HCC
2. Hepatic decompensation

Although pregnancy, overdose, cancer (excluding HCC), and potential drug induced liver injury (DILI) are not always serious by regulatory definition, these events must be handled as SAEs.

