7.5.2. Data collection procedures for adverse events

Participants will be interviewed regarding medical conditions, medication changes, and symptoms that have occurred at each study visit. An Adverse Event form will be completed if any adverse event is reported. If the study coordinator or a study physician learns of any hospitalizations or other adverse events between study visits, an Adverse Event form will be completed. All adverse events and Serious Adverse Events from time of study entry (consent) up to the end of follow-up (week 96) will be reported to the DCC.

A Serious Adverse Event form will be completed for all adverse events rated as serious.

Participants will be followed for all ongoing unresolved adverse events until they are either resolved, or in the opinion of the study physician, the participant is medically stable.

A study physician will assess the relationship of each adverse event to the use of study drug, based on available information, using guidelines outlined in the MOP.

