8.1.1. Analysis of primary endpoints

The primary endpoints include safety, measured by the rate of adverse and Serious Adverse Events, and efficacy, defined as loss of HBeAg and HBV DNA $\leq 1,000$ IU/mL at the end of follow-up (week 96). That is, only participants achieving HBeAg loss and having HBV DNA ≤ 1000 IU/mL at the end of follow-up will be considered as achieving the primary efficacy endpoint.

Safety

Summaries of adverse events (number of adverse events, number and percentage of participants with at least one adverse event, and for each adverse event, rate per person-years) will be provided. Events will be summarized based on the date of onset for the event. A treatment emergent adverse event will be defined as an adverse event that begins on or after the date of first dose of study drug.

Summaries of the following are planned:

- all adverse events recorded between screening and first dose of study medication,
- all treatment emergent adverse events,
- all emergent and related adverse events,
- all treatment emergent renal adverse events,
- all treatment emergent and related renal adverse events
- combined Grade 2, 3 and 4 treatment emergent adverse events,
- combined Grade 2, 3 and 4 related treatment and emergent adverse events,
- combined Grade 3 and 4 treatment emergent adverse events,
- combined Grade 3 and 4 related treatment and emergent adverse events,
- all adverse events that caused permanent discontinuation of study drug,
- all adverse events that caused temporary interruption of study drug,
- all serious adverse events, and
- all serious and related adverse events.

We will provide 95% confidence intervals for the rate of adverse and serious adverse events.

Efficacy

The percentage of participants achieving the primary efficacy endpoint will be summarized with the point estimate and 95% confidence interval.

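### Treatment-emergent adverse events are defined by onset date alone, so an event that starts between consent and first dose and worsens on drug can be missing from every treatment-emergent table

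*Combined protocol and SAP*

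**What the plan says.** - **Definition (section 8.1.1, Safety).** A "treatment emergent adverse event will be defined as an adverse event that begins on or after the date of first dose of study drug". The test is onset. A change in severity is not mentioned.
- **Placement in tables (section 8.1.1).** "Events will be summarized based on the date of onset for the event".
- **Collection window (section 7.5.2).** "All adverse events and Serious Adverse Events from time of study entry (consent) up to the end of follow-up (week 96) will be reported". The recipient is the data coordinating center. Events can therefore be on file before any drug is taken. Section 6.2 puts consent and screening within 6 weeks of baseline.
- **Pre-dose table (section 8.1.1).** One listed summary covers "all adverse events recorded between screening and first dose of study medication".
- **What counts as an adverse event (section 7.5.1).** It is "any adverse change from the participant's baseline (pre-treatment) condition", arising after consent, whether or not related to treatment.
- **Tables not tied to treatment emergence (section 8.1.1).** These include "all adverse events that caused permanent discontinuation of study drug", and the summaries of temporary interruption, serious events, and serious related events.

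Sections 2.2.1 and 8.1.1 make safety a primary endpoint, measured by rates of adverse and serious adverse events.

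**The concern.** A treatment-emergent definition is meant to capture what happens to participants once they are on drug. That includes new events and existing events that get worse. This definition covers only the first kind. Because collection starts at consent, a mild event recorded during screening has a pre-dose onset date, and the onset rule then keeps it out of the on-treatment tables whatever grade it later reaches.

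The rule matters for this regimen. Section 7.1 lists fatigue and depression among the common effects of peginterferon. Mild forms can be present at entry: section 4.2 excludes current depression only when moderate or severe, and section 7.1.1 makes a CES-D score above 15 at screening a reason to consider referral, not an exclusion.

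At stake is the severity profile of the regimen, reported from a single arm of 40 with no comparator. Any error goes one way, because the onset rule can remove on-drug worsening from the tables but cannot add to them.

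**Working it through.** **1. The plan's own figures.** The only design calculation is the precision table in section 8.3. The exact (Clopper-Pearson) 95% limits for x of n are:

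- lower = Beta quantile at 0.025 with parameters (x, n − x + 1)
- upper = Beta quantile at 0.975 with parameters (x + 1, n − x)

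With n = 40:

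| x/40 | Computed limits | Computed width | Section 8.3 |
|---|---|---|---|
| 6 (0.15) | 0.0571-0.2984 | 0.2413 | 0.057-0.298, 0.24 |
| 8 (0.20) | 0.0905-0.3565 | 0.2660 | 0.091-0.356, 0.27 |
| 10 (0.25) | 0.1269-0.4120 | 0.2850 | 0.127-0.412, 0.29 |
| 12 (0.30) | 0.1656-0.4653 | 0.2997 | 0.166-0.465, 0.30 |

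The plan's table reproduces to rounding. It concerns efficacy, and the present point does not depend on it. The same method is used in step 4. That is an assumption, since section 8.1.1 promises 95% intervals for safety rates without naming a method.

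**2. Sorting the planned safety summaries.** Section 8.1.1 lists 13:

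- 1 covers the period before first dose.
- 8 are treatment-emergent: all; related; renal; renal related; Grade 2-4; Grade 2-4 related; Grade 3-4; Grade 3-4 related. (The second is taken as treatment-emergent although its label says only emergent.)
- 4 are not limited to treatment-emergent events: permanent discontinuation, temporary interruption, serious, serious and related.

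1 + 8 + 4 = 13. All four grade-based summaries fall in the treatment-emergent group. None of the 13 covers dose reduction.

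**3. Following one event.** Take a grade 1 headache that starts after consent and before first dose, continues, and reaches grade 3 on treatment. It is not serious and is handled by a peginterferon dose reduction without a hold.

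| How the site records it | Onset on file | Pre-dose table | Treatment-emergent tables | Four unrestricted tables |
|---|---|---|---|---|
| One record, grade updated | Before first dose | Yes | None | None |
| New record at the worsening | After first dose | Original event only | Yes, including Grade 2-4 and Grade 3-4 | None |

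The same clinical course gives different tables depending on site practice. Section 7.5.1 permits the second row, because a worsening is an adverse change from the pre-treatment state. Section 7.5.2 fits the first row equally well: a form is completed when an event is reported, and unresolved events are followed until resolved or stable. Neither section says what to do when the grade changes.

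The dose-reduction case is realistic. Section 7.2.1 says every effort will be made to keep participants on peginterferon through dose reduction. Section 5.3.3 cites dose modification in 31% to 47% of patients in the hepatitis B registration trials, against discontinuation in 6% to 9%. It also says that laboratory abnormalities were the most frequent reason for adjustment, so these percentages do not measure how often a symptom worsens.

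**4. Size, by assumption.** The documents give no count of worsened pre-dose events. Let b participants have a Grade 3-4 event that the present definition counts, and let k more have only a worsened pre-dose event at that grade. The present rule gives b/40 and the amended rule gives (b + k)/40. Each such participant adds 1/40 = 2.5 percentage points.

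| b | k = 0 | k = 1 | k = 2 | k = 4 |
|---|---|---|---|---|
| 4 | 10% (2.8-23.7) | 12.5% (4.2-26.8) | 15% (5.7-29.8) | 20% (9.1-35.6) |
| 8 | 20% (9.1-35.6) | 22.5% (10.8-38.5) | 25% (12.7-41.2) | 30% (16.6-46.5) |

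A participant who already has another counted Grade 3-4 event does not change the participant percentage. Only the event count and the person-year rate are then too low.

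**The case against.** The strongest reply is that section 7.5.1 already solves the problem. A baseline symptom that becomes severe on drug is an adverse change from the pre-treatment condition, so it is a new event with an on-treatment onset, and section 7.5.2 calls for a form. The manual of operations, which section 9.1 cites alongside section 7.5 for definitions and management guidelines, may also hold a recording rule that is not visible here. This reply stands in part: a reader might infer that a worsened event always drops out of every treatment-emergent table, and the documents do not support that. What remains is that no section requires a new record, and the analysis definition itself looks only at onset.

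Three other stronger readings also go too far.

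- **That serious event rates are understated too.** The serious, serious related, discontinuation and interruption tables are not limited to treatment-emergent events, so a worsened event of those kinds is still shown. This includes depression that stops peginterferon (section 7.1.1).
- **That former controls are the worst affected.** Section 6.13 says that those "who were randomized to the control (no treatment) group will be offered treatment if they still meet the entry criteria for this trial", but it also provides for a fresh consent and a schedule starting again at Day 0. Whether events from the control period carry over with their old dates is not stated, so the documents cannot rank this group.
- **That fatigue and low mood are common before treatment, so the bias is large.** No section gives a pre-treatment frequency.

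The affected set is also narrow. For a new participant the event must start in a window of at most 6 weeks, be ongoing at first dose, worsen later, and not be logged again. Drug starts with entecavir on Day 0, so events that begin during the 8-week lead-in already count. A symptom that predates consent falls outside the adverse event definition until it worsens, and that worsening could then count as new.

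**Conclusion.** The point holds as a defect in the definition, with limited reach. As written, an event that starts between consent and first dose and is kept as one record is excluded from all eight treatment-emergent summaries, and so from every summary by grade, however severe it becomes on drug. Whether that happens is left to site practice. The remaining understatement mainly concerns non-serious worsening that neither stops nor interrupts drug. Such an event would appear only in the pre-dose table.

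The direction is known: on-drug severity can only be understated. The amount is not known from the documents. The move from 10% to 12.5%, 15% or 20% assumes 4 of 40 counted participants and 1, 2 or 4 missed ones, and both numbers are illustrative. Even the largest of these shifts stays inside the exact interval around the 10% estimate (2.8-23.7%). The case for correction is therefore that the error is systematic and avoidable in a primary endpoint, not that it is shown to be large. Efficacy, sample size and the planned interval calculations are unaffected.

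**What to change.** - **Section 8.1.1.** Define a treatment-emergent adverse event as one that starts, or increases in grade, on or after the day of the first dose of study drug. State that it is tabulated at its maximum post-dose grade.
- **Adverse event form instructions.** Require sites to record the date of any grade increase after first dose, or to log the increase as a new event dated at the worsening. Choose one method for all sites.
- **Former controls.** State whether events from the control period stay on file with their original dates after reconsent and the new Day 0.

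The cost is one amended sentence in section 8.1.1, one added line on the form and a short clarification for former controls. Reported treatment-emergent rates may be slightly higher. Visits, treatment and sample size do not change.

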2.1 Primary objectives

- To determine the safety and efficacy of treatment with 8 weeks of entecavir followed by 40 weeks of both entecavir and peginterferon alfa-2a in the treatment of chronic hepatitis B in HBeAg positive adults who are in the immune tolerant phase.
- To evaluate “off treatment” safety and sustained responses after treatment with entecavir and peginterferon alfa-2a in the treatment of chronic hepatitis B in HBeAg positive adults who are in the immune tolerant phase.

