2.2 Primary endpoint

2.2.1 Safety: Adverse Events and Serious Adverse Events through the end of treatment and through the end of follow-up

2.2.2 Efficacy: HBeAg loss (lack of detectable HBeAg) AND HBV DNA $\leq 1,000$ IU/mL 48 weeks after stopping therapy.

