5.1 Dosage and administration

Treatment Entecavir 0.5 mg daily orally for 48 weeks plus peginterferon alfa-2a 180 µg subcutaneously (sq) weekly during weeks 9-48 of treatment. After treatment discontinuation, follow-up off treatment will be for 48 weeks.

Participants will be instructed to take one tablet of entecavir daily on an empty stomach at least 2 hours prior to or after meals. Participants will be instructed to take 180 µg of peginterferon alfa-2a subcutaneously once weekly. The participant will be instructed to inject the peginterferon alfa-2a on the same day each week.

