7.3. Managing adverse effects of entecavir

7.3.1. Adverse effects of entecavir

- Headache, fatigue, dizziness, nausea, upper abdominal pain, upset stomach, diarrhea, vomiting, trouble sleeping or sleepiness, changes to liver and pancreas enzymes. These side effects were generally mild to moderate in severity.
- Lactic Acidosis: Patients taking drugs similar to entecavir have experienced lactic acidosis. Symptoms of lactic acidosis include weakness/tiredness, muscle pain, trouble breathing, stomach pain with nausea and vomiting, feeling cold (particularly in extremities), dizziness/lightheadedness, and increased heart rate.
- Hepatitis "flares": In patients with chronic hepatitis B, liver enzyme changes are common.
- Laboratory studies have shown that entecavir does not interact with the enzymes in the liver that are responsible for most drug interactions. However, because the body gets rid of entecavir in the urine, it is possible that drugs which affect kidney function could increase the levels of entecavir when a patient uses both drugs. These types of drugs are not allowed in this study.
- When mice and rats were given entecavir for their entire adult life, these animals developed more tumors, including cancerous tumors, than are normally expected. Male mice developed non-cancerous lung tumors when they were exposed to entecavir at levels greater than or equal to 4 times higher than participants will be exposed to in this study. Cancerous lung tumors were also observed in male and female mice when they were given high levels of entecavir. Further animal studies have been performed to better understand these findings. These additional studies suggest that the lung findings in mice are unique for mice. The lung findings in mice did not occur in rats, dogs or

monkeys. It is not known whether these tumor findings in animals are relevant to humans who are treated with Entecavir.

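### Treatment-emergent events have no end date in 8.1.1, so the safety summaries pool time on and off drug and give no off-treatment result for a primary objective

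*Combined protocol and SAP*

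**What the plan says.** Off-treatment safety is a primary objective: the second bullet of section 2.1 covers off-treatment "safety and sustained responses after treatment with entecavir and peginterferon alfa-2a". Section 2.2.1 then sets the primary safety endpoint as "Adverse Events and Serious Adverse Events through the end of treatment and through the end of follow-up", which names two windows.

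Section 8.1.1 is the analysis of that endpoint. A treatment-emergent event is "an adverse event that begins on or after the date of first dose of study drug". The planned measures are the number of events, the number and percentage of participants with at least one, and "for each adverse event, rate per person-years", with 95% confidence intervals for the rates. On timing it adds "Events will be summarized based on the date of onset for the event", but the only periods it names are before and after first dose. It does not define the person-time.

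Treatment lasts 48 weeks (section 5.1), and "After treatment discontinuation, follow-up off treatment will be for 48 weeks". Section 7.5.2 has adverse events reported from consent to week 96.

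**The concern.** Under the 8.1.1 definition an event at week 90, 42 weeks after a scheduled last dose, is treatment emergent and sits in the same row as an event on drug. Two different hazards are at issue: interferon toxicity during dosing, and hepatitis flare after withdrawal. The protocol itself separates them when it manages ALT rises, with section 6.11 for the treatment phase and 6.12 for follow-up. Section 7.3.1 lists flares among the adverse effects of entecavir and notes that "In patients with chronic hepatitis B, liver enzyme changes are common".

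If the summaries are produced as listed, a reader cannot tell a regimen that is mostly toxic on drug from one that mostly causes trouble after stopping. The primary objective on off-treatment safety would then have no planned result.

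**Working it through.** **The listed summaries.** Of the 13 in 8.1.1, one is pre-dose, eight are treatment-emergent, two concern events that led to stopping or interrupting drug (on-treatment by nature), and two are serious-event rows with no stated window. None is cut at the end of treatment.

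**The plan's own figure.** The plan computes nothing for safety. Its only computed precision is for efficacy (section 8.3). Exact Clopper-Pearson limits for 10/40 are 0.127 to 0.412, width 0.29, as stated there. The same method is used below.

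**Person-years.** Inputs: 40 participants (8.3), and 48 weeks on and 48 off (5.1). Assumptions: full follow-up, person-years counted over the whole period from first dose, and 52.18 weeks per year.
- On treatment: 40 × 48 / 52.18 = 36.8. Off treatment: 36.8. Pooled: 73.6.

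**Pooled rate.** With equal person-time, pooled = (on rate + off rate) / 2. If the off rate is ρ times the on rate, pooled/on = (1 + ρ)/2 and pooled/off = (1 + ρ)/(2ρ).

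| ρ (assumed) | pooled ÷ on rate | pooled ÷ off rate |
|---|---|---|
| 0 | 0.50 | – |
| 0.1 | 0.55 | 5.5 |
| 0.25 | 0.625 | 2.5 |
| 0.5 | 0.75 | 1.5 |
| 1 | 1.00 | 1.0 |

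The pooled rate is half the true one only when all events fall in one period. Otherwise, unless the two rates are equal, it is too low for one period and too high for the other. If 20% were lost at week 72 (assumed), on-time is 1920 weeks and off-time is 32 × 48 + 8 × 24 = 1728. For a hazard confined to one period, the factors become 3648/1920 = 1.90 on treatment and 3648/1728 = 2.11 off.

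**Illustration (assumed counts).** Eight participants have one flare each. Rates are per 100 person-years with exact Poisson 95% intervals; percentages have Clopper-Pearson intervals.

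| | 6 on, 2 off | 2 on, 6 off |
|---|---|---|
| Pooled rate, 8/73.6 | 10.9 (4.7–21.4) | 10.9 (4.7–21.4) |
| Pooled participants, 8/40 | 20% (9.1–35.6%) | 20% (9.1–35.6%) |
| Off-treatment rate | 2/36.8 = 5.4 (0.7–19.6) | 6/36.8 = 16.3 (6.0–35.5) |
| Off-treatment participants | 2/40 = 5% (0.6–16.9%) | 6/40 = 15% (5.7–29.8%) |

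The pooled entries are identical. In the first column the on-treatment rate is 16.3, so the pooled rate is 16.3/10.9 = 1.5 times too low for on-treatment time and 10.9/5.4 = 2.0 times too high for off-treatment time.

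**What the nested windows would recover.** Suppose first dose to end of treatment and first dose to week 96 were both tabulated.
- Events and person-years subtract: 8 − 6 = 2 events over 73.6 − 36.8 = 36.8 person-years, or 5.4 per 100.
- Participants do not subtract, because someone with an event in each period counts once. If the windows show 6/40 and 8/40, at least 8 − 6 = 2 participants had an off-treatment event. All six earlier participants could have had another, so the maximum is 2 + 6 = 8.

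**The case against.** The strongest reply is that this is one combined document. Section 2.2.1 already names both windows, 8.1.1 is headed as the analysis of that endpoint, and assigning events by onset date is what would fill those windows. Much of this stands. Nothing in 8.1.1 revokes 2.2.1, and with both windows tabulated the off-treatment event rate follows by subtraction. It does not close the gap: 8.1.1 lists no end-of-treatment table, names no cut-point, and the nested windows still leave the off-treatment participant count unknown.

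A reader might infer that the planned tables understate every safety result by a factor of two. The documents do not support that. The factor applies only to a rate for a hazard confined to one period. Event counts and participant percentages are not diluted at all; they just do not show when events occurred. Even the rate depends on an undefined denominator: with on-treatment exposure only, the eight flares would give 8/36.8 = 21.7 per 100 person-years, an overstatement.

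A reader might also infer that ALT flares after stopping would go unseen. Section 8.1.2.2 summarises ALT change at treatment and follow-up time points, and sections 2.3.1 and 2.3.2 set ALT thresholds at weeks 48 and 96. These separate ALT by period, but they do not count participants with flares and do not cover other events. That every flare would be recorded as an adverse event is itself an inference, because the limits in 6.11 and 6.12 trigger management and do not define an event.

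Finally, this is a descriptive pilot with no safety test, and the monitoring board receives cumulative summaries every three months (section 9.1). That limits the consequence. Those summaries are specified only overall and by seriousness, so they do not supply the missing split.

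**Conclusion.** The point holds as a gap between a primary objective and its analysis. The treatment-emergent summaries in 8.1.1 pool 48 weeks on drug with 48 weeks off, and no listed summary reports the end-of-treatment window of 2.2.1 or off-treatment safety for 2.1.

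If person-years cover the whole period and follow-up is complete, each pooled rate is the average of the two period rates, with the error ranging from none (equal rates) to a factor of two (all events in one period) relative to the higher of the two. The loss that even the 2.2.1 windows cannot repair is the number of participants with an off-treatment event, anywhere from 2 to 8 of 40 in the illustration. The flare counts are assumed; the equal weighting follows from the 48 + 48 week design.

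It is worth settling before the data are summarised, but it is not fatal: onset dates are collected, so the split can be made without new data.

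**What to change.** In 8.1.1 keep the treatment-emergent definition for an overall column. Add two columns, assigned by onset date, to each treatment-emergent summary and each serious-event summary:

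- **On treatment:** first dose to last dose of either drug, whichever is later. This covers participants who stop one drug and continue the other under 7.5.4.
- **Off treatment:** after that dose to the last follow-up visit, or to the start of any retreatment under 6.12.3. List events after retreatment separately.

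In each column give participants with at least one event (n/N with an exact 95% interval, N being those entering the period) and the rate over that period's own person-years. State the person-year definition for the overall column as well. Add a footnote that events within about 33 days of the last peginterferon dose may reflect residual drug (section 5.3.1 gives a 160-hour half-life; 5 × 160 / 24 = 33 days).

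The cost is a few sentences and two columns, from onset and dosing dates already collected. Each column has smaller numbers and wider intervals, and some late peginterferon effects will be counted as off-treatment. The on-treatment column also still contains the 8 entecavir-only weeks, so a rate for toxicity confined to the peginterferon weeks remains diluted by 48/40 = 1.2, against 96/40 = 2.4 when everything is pooled.
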